9.2. Rescue Medication

Subjects will be provided with acetaminophen at each clinic visit to use as a rescue medication for breakthrough pain in the target knee, and subjects will be instructed to use the acetaminophen only if the pain in the target knee is of sufficient severity to require use of the rescue medication. No acetaminophen use is permitted from the 2 days before to the end of each study visit. Subjects will be asked to bring the acetaminophen container(s) with any remaining tablets to the next visit.

Temporary use of over-the-counter acetaminophen is allowed for the treatment of other AEs, except for the periods from the 2 days before to the end of each study visit. The use of over-the-counter acetaminophen should be limited to up to 3 days between each visit for Visits 1 through 4, up to 5 days between each visit for Visits 4 through 9, and up to 20 days between each visit for Visit 9 through 11. Subjects should report all over-the-counter acetaminophen use to the investigator at each visit.

Subjects will be advised to limit their total acetaminophen use, from both the study-provided acetaminophen and over-the-counter sources, to 3000 mg/day. Subjects will be required to abstain from all use of acetaminophen from the 2 days before to the end of each study visit.

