13. STATISTICS

13.1. Power and Sample Size Determination

Approximately 80 subjects with symptomatic primary OA of the knee will be randomized. Forty subjects per group (80 total subjects) were calculated to provide an 80% probability that a 3 mm (or greater) treatment difference point effect for the primary endpoint will be observed, but not necessarily at a statistically significant level. This assumes that the true treatment difference is 7.5 mm and standard deviation is 23 mm based on the previous Japanese 613/1022 study.

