13.2. Randomization

Immediately prior to injection at Week 0, subjects who meet all eligibility criteria will be randomized to a treatment group using a 1:1 ratio of SI-613:placebo.

Subjects will be randomized using a dynamic procedure by a minimization protocol, ¹⁰ balancing treatment assignment on K-L score, baseline WOMAC VAS pain score, sex, and investigational site.

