13.4.3. Efficacy Analyses

13.4.3.1. Primary Efficacy Analysis

The primary efficacy analysis will be performed on the WOMAC VAS pain subscore using longitudinal analysis to incorporate information from pain scores assessed at Weeks 1, 2, 4, 6, 8, 10, and 12. A direct likelihood approach as implemented in the SAS MIXED procedure will be used to estimate model parameters designed to reflect group-specific mean values over time. The primary efficacy hypothesis concerns the over a 12-week evaluation period from Week 1 to Week 12, and the group comparison is defined as the average effect over assessments during these weeks. Supporting analyses involve comparisons reflecting group differences at the various study visits, including landmark analysis at Week 12 and early onset of efficacy at Week 1. In all cases, model parameters will be used to determine comparisons for which statistical significance against null zero hypotheses and corresponding 95% confidence intervals will be provided. The basic longitudinal model will be specified as a repeated-measures model that expresses the pain score as a linear function of treatment, time, treatment-by-time interaction, and clinically relevant covariates (pretreatment pain measurement, K-L score, and sex) and a fixed-site effect.

The model is designed to account for correlations among responses over time and to use these correlations to implicitly impute missing values from the non-missing values. The type=UN option in the SAS MIXED procedure will be used to model correlation patterns across time.

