13.4.3.2. Secondary Efficacy Analyses

A longitudinal analysis model will be used as described in the primary efficacy analysis for the analysis of WOMAC VAS physical function subscore, WOMAC VAS stiffness subscore, WOMAC VAS total score, PGIC, CGIC, SF-36 scores, weekly average of daily pain scores, and PASE scores.

Continuous responder analysis with WOMAC VAS pain subscore will be performed, and differences between the SI-613 and placebo groups in the percentages of subjects experiencing a >30% or >50% improvement in WOMAC VAS pain subscore will be analyzed with Fisher's exact test. For the analysis of the percentages of OMERACT-OARSI responders, 11,12 differences between the SI-613 and placebo groups in the percentages of positive responders over 12 weeks will be analyzed with generalized estimating equations (GEE) model. For each post-treatment study visit, subjects will be defined as responders or nonresponders based on the OMERACT-OARSI set of criteria. These repeated binary outcomes (responders/nonresponders) will be modeled with GEE, with the relevant pretreatment covariate of pain (average WOMAC VAS pain score from Visits 1 and 2), clinically relevant covariates (K-L score and sex), and a fixed-site effect. A Wald test based on the estimated regression parameter for treatment group assignment will be used for hypothesis testing for this secondary efficacy objective. For the analysis of the percentages of positive responders, subjects who discontinue from the study prior to Week 12 because of either target knee-related AEs or lack of efficacy will be classified as not improved subjects or nonresponders in the efficacy analysis.

For the analysis of the amount of acetaminophen rescue medication consumed for the target knee, the percentages of subjects using rescue medication will be presented. The analysis of the overall use of acetaminophen rescue medication over 12 weeks will be conducted in the analysis of covariance

(ANCOVA) model of the change from baseline of acetaminophen usage. The baseline acetaminophen usage, K-L score and sex will be included as covariates in the ANCOVA model.

Efficacy analyses will be repeated by using entire period from Week 1 to Week 26.

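### The acetaminophen ANCOVA leaves out baseline WOMAC pain and site, two of the four minimisation factors carried by the primary and OMERACT-OARSI models

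*Combined protocol and SAP*

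**What the plan says.** Section 13.2 assigns treatment 1:1 by a dynamic minimisation procedure, "balancing treatment assignment on K-L score, baseline WOMAC VAS pain score, sex, and investigational site". Section 5 names the same four factors.

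Section 13.4.3.1 gives the primary model treatment, time and their interaction, together with "clinically relevant covariates (pretreatment pain measurement, K-L score, and sex) and a fixed-site effect". Section 13.4.3.2 carries the primary approach over to WOMAC function, stiffness and total score, PGIC, CGIC, SF-36, weekly average daily pain and PASE. For the OMERACT-OARSI GEE it lists pretreatment WOMAC pain (the Visit 1 and 2 average) and then "clinically relevant covariates (K-L score and sex), and a fixed-site effect".

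For rescue use over 12 weeks the same section plans an ANCOVA of change from baseline and states: "The baseline acetaminophen usage, K-L score and sex will be included as covariates in the ANCOVA model". WOMAC pain and site are not mentioned. The section ends: "Efficacy analyses will be repeated by using entire period from Week 1 to Week 26", so the same model is also used over the longer period.

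Rescue consumption is a listed secondary objective (section 4.2). It is tested at the two-sided 5% level (section 13.5.1) without multiplicity adjustment (section 13.5.4).

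**The concern.** When allocation is balanced on a factor, the treatment difference varies less from trial to trial than it would under simple randomisation. A linear model that omits the factor still counts its variance as noise, so the standard error is too large for the design actually used. If the factor is prognostic, the test is conservative and power is lost.

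Both omitted factors could plausibly matter here. The plan itself classes pretreatment pain as clinically relevant in its primary model. Section 9.2 also tells subjects to "use the acetaminophen only if the pain in the target knee is of sufficient severity to require use of the rescue medication", which ties rescue use to target knee pain. Site could matter if instructions or habits of rescue use differ between centres. Baseline usage is a sensible covariate, but it is not a minimisation factor and it does not stand in for site.

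What is at stake is precision on one secondary endpoint, and consistency with the plan's other covariate-adjusted models.

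**Working it through.** **1. Covariate lists side by side**

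| Model | K-L | Sex | WOMAC pain | Site |
|---|---|---|---|---|
| Minimisation (13.2) | yes | yes | yes | yes |
| Primary model (13.4.3.1) | yes | yes | yes | yes |
| OMERACT-OARSI GEE (13.4.3.2) | yes | yes | yes | yes |
| Acetaminophen ANCOVA (13.4.3.2) | yes | yes | no | no |

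The ANCOVA carries 2 of the 4 factors. It is the only covariate-adjusted efficacy model in the text that is specified without pain and site.

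**2. The plan's own figure.** Section 13.1 assumes that "the true treatment difference is 7.5 mm and standard deviation is 23 mm", with 40 per group, and states an 80% probability of observing at least 3 mm. SE = 23 × √(2/40) = 5.14 mm; (7.5 − 3)/5.14 = 0.875; Φ(0.875) = 0.809. The figure reproduces. It concerns WOMAC pain; the documents give no figure for acetaminophen.

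**3. Effect sizes used.** 7.5/23 = 0.33 SD is the only standardised effect derivable from the documents, and it is borrowed from the primary endpoint. An effect of 0.5 SD is added as a second case. With 40 per group the SE is √(2/40) = 0.2236 SD. Two-sided 5% power by the normal approximation is Φ(0.326/0.2236 − 1.96) = 31% and Φ(0.5/0.2236 − 1.96) = 61%.

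**4. Hand calculation of the best case.** Let pain and site each explain a share r of the variance beyond baseline usage, and suppose minimisation balances both perfectly. The true SE is then 0.2236 × √(1 − 2r), while the planned model reports 0.2236. At r = 10% the true SE is 0.2236 × √0.80 = 0.200.
- Planned test, type I error: 2 × Φ(−1.96/√0.80) = 2.8%.
- Planned power: Φ((0.5 − 1.96 × 0.2236)/0.200) = 62%; at 0.33 SD, 29%.
- Adjusted power: Φ(0.5/0.200 − 1.96) = 71%; at 0.33 SD, 37%.

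That is a gain of about 8 points before allowing for degrees of freedom spent on site, pooling of small sites and imperfect balance. The same formulas at r = 5% give about 4 points.

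**5. Simulation with those costs included.** N = 80; minimisation on the four factors (pain in two levels) with probability 0.8; unequal sites; sites with fewer than 6 subjects pooled; pain bounded to reflect the 50–90 mm entry range (section 6.1); baseline usage, K-L and sex in every model; 6,000 replicates per scenario. Monte Carlo SE is about 0.3 points for size and 0.6 for power. Entries are as planned → with pain and site added.

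| Sites | r | Type I error | Power, 0.33 SD | Power, 0.5 SD |
|---|---|---|---|---|
| 8 | 0 | 5.2 → 5.1% | 29 → 28% | 58 → 56% |
| 8 | 5% | 3.9 → 4.7% | 30 → 32% | 60 → 62% |
| 8 | 10% | 4.1 → 5.0% | 29 → 33% | 60 → 65% |
| 16 | 0 | 4.9 → 5.0% | 30 → 29% | 59 → 57% |
| 16 | 5% | 4.8 → 5.2% | 30 → 31% | 60 → 61% |
| 16 | 10% | 3.5 → 4.5% | 29 → 33% | 61 → 66% |

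Mean null estimates lie within 0.01 SD of zero. With 16 sites entered unpooled and r = 0, power falls from 30% to 26% (0.33 SD) and from 59% to 53% (0.5 SD).

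**6. Sensitivity to the assumptions.** A 3,000-replicate run at r = 10% gave 59 → 67% and 28 → 35% with 8 sites, and 61 → 64% and 28 → 33% with 16 (0.5 and 0.33 SD; Monte Carlo SE about 0.9 points). The gains are 8, 7, 3 and 5 points, averaging about 6. A run with 6 sites and minimisation probability 0.9 gave 61 → 68% at r = 10% and 0.5 SD, and 61 → 81% at r = 20%. Across all runs with r = 10%, the planned test's type I error lay between 2.4% and 4.1%.

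**The case against.** The strongest reply is that this is a preference, not a flaw. The estimate is unbiased and the test keeps its level. The endpoint is secondary with no multiplicity control, and the trial is not sized for significance. The plan has no rule that every analysis must carry all the minimisation factors: the analyses of more than 30% and more than 50% improvement use Fisher's exact test, with no covariates. The ANCOVA can also be read as coherent. In the primary model, pretreatment pain is the outcome's own baseline, and here baseline usage takes that place. Pain at entry is confined to 50–90 mm, which limits what it can explain. With 80 subjects, small sites are a fair reason for leaving site out. Finally, section 13.3 refers some detail to a statistical analysis plan, which might add covariates.

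Much of this stands. It limits the point to precision, and the gain depends on prognostic strengths that the documents do not give. Four things remain:
- The Fisher tests take no covariates at all, so they do not explain why a covariate-adjusted model carries two of the factors and drops two.
- Baseline usage may carry part of the information in pain, but it has no bearing on site.
- Pooling answers the small-site difficulty, and the primary model already commits to a fixed site effect.
- The supplied text lists the ANCOVA covariates outright and gives no reason for the difference. If another document adds pain and site, the point is closed.

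**Conclusion.** The mismatch is real and its consequence is modest. Under the assumed 8 to 16 sites with small sites pooled, adding both factors gains about 4 to 7 points of power if each explains 10% of the variance beyond baseline usage (single simulated cells run from 3 to 8). It gains about 0 to 2 points at 5% and costs about 0 to 3 if neither is prognostic. Site number, minimisation probability, prognostic strength and the effect on tablet use are all assumptions.

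A reader might infer that omitting minimisation factors biases the comparison or makes a false positive more likely. It does neither: in a linear model with balanced allocation the estimate stays centred, and the error in size is towards conservatism. A reader might also take the 61 → 81% result as the expected gain. It needs pain and site to explain 20% each, which nothing in the documents supports. Nor should a reader infer that subjects who leave early will be scored as low users: the text does not say that unscaled tablet totals will be analysed.

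The change is worth making because it is cheap and brings the model into line with the plan's other covariate-adjusted analyses. It does not affect the primary analysis or the sample size.

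**What to change.** In section 13.4.3.2, extend the acetaminophen ANCOVA covariates to baseline acetaminophen usage, baseline WOMAC VAS pain (average of Visits 1 and 2), K-L score, sex and a fixed site effect. State before unblinding how small sites are pooled, for example by combining sites below a set number of subjects. Apply the same model to the Week 1–12 and Week 1–26 analyses.

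The cost is one or two sentences and minor programming; pain and site are already collected, so no new data are needed. The downside is about 0 to 3 points of power if neither factor predicts rescue use. Without pooling it is larger: about 4 to 6 points with 16 sites (30% to 26% and 59% to 53%).

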13.4.3.3. OMERACT-OARSI Responder

A subject will be considered an OMERACT-OARSI responder if he or she meets criteria for improvement in WOMAC VAS pain subscore, WOMAC VAS physical function subscore and PGIC.

13.4.4. Safety Analyses

Treatment-emergent AEs (any AEs recorded during or following the study injection) will be summarized by treatment group and categorized by severity, time of occurrence, and relationship to the study procedures and to the investigational product. If a subject has more than 1 occurrence of the same AE, he/she will be counted only once within that preferred term in the summary tables. The most severe occurrence of an AE, as well as the most extreme relationship of the AE to the study procedures and investigational product, will be indicated in cases of multiple occurrences of the same AE. Serious adverse events and target knee AEs also will be summarized separately. All AEs will be presented in a listing. Additionally, listings of SAEs and AEs leading to discontinuation will be generated.

Target knee examination and synovial assessments will be summarized by treatment group. In addition, these relationships will be analyzed.

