7.2. Study Procedures

7.2.1. Screening / Visit 1 (Week -2 to -1; Day -14 to -7)

Screening (Week -2 to -1) will occur 7 to 14 days prior to Visit 2 (Week 0).

The following procedures will be performed at Screening / Visit 1:

- Prior to any study-specific procedures, obtain written informed consent for this study.
- Perform screening inclusion/exclusion criteria eligibility assessments, which include the following:
 - Onfirm that the subject has not used any prohibited medications or therapies within the protocol-defined washout windows. If a subject has used prohibited or restricted medications or therapies within the washout window, the subject may remain in the study and return after the appropriate washout period to continue the Screening visit.
 - Record the use of prior and current concomitant medications and therapies, confirming that the subject has been on a stable dose and regimens of chondroitin sulfate or glucosamine for at least 15 days and a stable regimen of physical therapy for at least 29 days. If a subject has used varied doses of chondroitin sulfate or glucosamine within the past 15 days inclusive or a varied regimen of physical therapy within the past 29 days inclusive, the subject may begin a period of stable dosing/regimen and return after ≥15 days or ≥29 days, respectively, to recomplete the activities in the Screening visit.
 - Collect demographic data and medical history information, including diagnosis and history of OA.
 - Collect vital signs.
 - Measure the subject's height and weight and use these data to calculate the subject's BMI.
 - o If no x-rays are available from the preceding 6 months, obtain an AP x-ray of the target knee joint with the subject in the standing position.
 - o Assess K-L score.
 - o Assess femoral-tibial angle (FTA).
 - Collect urine sample for a urine drug screen and for laboratory tests (qualitative urinalysis regarding glucose, protein and urobilinogen).
 - o Collect blood sample for laboratory tests (complete blood count, complete metabolic profile, blood alcohol content, and hepatitis screening).
 - For females of childbearing potential, collect a blood sample to perform a serum pregnancy test.

- Record baseline signs and symptoms as baseline for future potential AEs.
- Perform examination of the target knee.
- Assess patellar grinding via Clarke's test.
- Administer the WOMAC.
- Conduct the 50-foot walk test and measure pain immediately following using a 100-mm VAS.

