Injection			X				X			X					
Distribute Subject Daily Diary	X	X		X	X	X		X	X		X	X	X		
Distribute Acetaminophen	X	X		X	X	X		X	X		X	X	X	X^{12}	
End of Study Form														X	

BMI = body mass index; CGIC = Clinical Global Impression of Change; FTA = femoral-tibial angle; K-L = Kellgren-Lawrence; PASE = Physical Activity Scale for the Elderly; PGIC = Patient Global Impression of Change; SF-36 = 36-Item Short Form Health Survey; WOMAC = Western Ontario and McMaster Universities Osteoarthritis Index * In principle, subjects are injected within 50 days after informed consent.

¹ Subject need to be suspend the use of rescue medication from the 2 days before to the end of the each clinic visit.

² Subjects who agree to discontinue use of the prohibited medications and therapies may return to complete screening after the described washout periods, as described in Section 9.3.

³ Subject cannot have used any prohibited medications or therapies and has not changed the dose and/or regimen of restricted medications or therapies since the previous visit.

⁴ Vital signs will include systolic and diastolic blood pressure, pulse rate, respiratory rate, and temperature.

⁵ X-ray is required if subject has not had an x-ray within 6 months of Visit 1 (Screening).

⁶ Laboratory tests at Screening will include complete blood count (CBC), complete metabolic profile, qualitative urinalysis, blood alcohol content, and hepatitis screening. Laboratory tests at other visits will include CBC, complete metabolic profile and qualitative urinalysis. Qualitative urinalysis is for glucose, protein and urobilinogen.

⁷ Women of childbearing potential only. A serum test will be performed at Screening, and a dipstick urine test will be performed prior to each injection and at the final study visit/early termination.

⁸ Adverse events (AEs) will be assessed twice at each in-person study visit: once at the beginning to capture AEs that have occurred since the last study visit, and once at the end to capture any AEs resulting from the study procedures.

⁹ WOMAC visual analog scale; pain subscore and pain following a 50-foot walk test are assessed for the target and contralateral knees at the Screening visit and before injection on Day 1. Other visits will include WOMAC assessment of the target knee only.

¹⁰ MRI at the screening visit will be conducted between Day -14 to Day -3.

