11.6. Medical History

11.6.1. General Medical History

A brief medical history will be recorded, including the following:

- All concomitant diseases that the subject is experiencing at the time of informed consent;
- Musculoskeletal diseases of the lower extremities that required surgery;
- Other musculoskeletal diseases of the lower extremities in the 1 year prior to Screening; and
- Other diseases that the investigator considers to be important.

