12.5.1. Definitions of Adverse Events/Effects

12.5.1.1. Adverse Event

An AE is defined as any untoward or unfavorable medical occurrence associated with the subject's participation in the research, whether or not considered related to the subject's participation in the research (ICH Guideline E6: Guideline for Good Clinical Practice). Any medical condition that is present at the time that the subject is screened will be considered as medical history and not recorded as an AE; however, if the condition worsens at any time during the study, it will be recorded and reported as an AE.

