12.5.3. Relationship to Investigational Treatment

An investigator's causality assessment is the determination of whether there exists a reasonable possibility that the investigational product caused or contributed to an AE and must be provided for all AEs (serious and non-serious).

Seikagaku Corporation's determination of attribution will be used for reporting to the appropriate health authorities. The relation of an AE to study participation will be determined using the descriptors and definitions provided in Table 3.

Table 3: Attribution of Adverse Events

Not Related	The AE is clearly/most probably caused by other etiologies such as participant's underlying condition, therapeutic intervention or concomitant therapy, or the delay between administration and the onset of the AE is incompatible with a causal relation, or the AE started before administration (screening phase). Therefore, there is not a reasonable possibility that the AE was caused by the investigational product.
Related	There is a reasonable possibility that the AE was caused by the investigational product. The expression "reasonable possibility" is meant to convey in general that there are facts (evidence) or arguments to suggest a causal relationship (21 CFR 312.32(a)).

The investigator should decide whether, in his or her medical judgment, there is a reasonable possibility that the event may have been caused by the investigational product. Any AE that is suspected to be related to the investigational product will be classified as an adverse drug reaction.

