12.5.4. Collecting and Recording Adverse Events

12.5.4.1. Period of Collection

All AEs, regardless of severity and/or the time of occurrence during the study, are to be recorded on the appropriate AE pages (either "serious" or "non-serious") in the eCRF. Recording of AEs will begin immediately upon a subject's signing the informed consent form and continue through the final study visit. Recording of any adverse drug reaction will continue until the event resolves or stabilizes. The investigator should complete all the details requested, including dates of onset, severity, action taken, outcome, and relationship to investigational product. Each event should be recorded separately.

All AEs and SAEs should be treated as medically appropriate. Adverse events should be followed until stabilization or the final study visit; adverse drug reactions should be followed until resolution or stabilization; and SAEs (regardless of suspected relationship to the investigational product) should be followed until the event resolves, stabilizes, or becomes non-serious.

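### Section 13.4.4 defines treatment emergence by when an AE is recorded, so an AE first recorded before the first injection that worsens afterwards can fall outside the by-arm summary

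*Combined protocol and SAP*

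**What the plan says.** Incidence of treatment-emergent AEs is the first item under the safety objective (4.3). The definition is in 13.4.4: "Treatment-emergent AEs (any AEs recorded during or following the study injection". The parenthesis ends there. It mentions neither onset nor worsening, and it uses the singular, although 8.4 schedules injections at Weeks 0, 4 and 8.

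Three other sections decide what becomes an AE in the first place:

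- 12.5.1.1: "Any medical condition that is present at the time that the subject is screened will be considered as medical history", and so is not an AE. The same sentence adds that "if the condition worsens at any time during the study, it will be recorded and reported as an AE".
- 12.5.4.1: "Recording of AEs will begin immediately upon a subject's signing the informed consent form". Each event gets its own record, with onset date and severity.
- 11.6.1: the history takes in "All concomitant diseases that the subject is experiencing at the time of informed consent".

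On timing, 7.2.1 puts consent before every study procedure. It lets a subject who has used a prohibited drug stay in the study and "return after the appropriate washout period to continue the Screening visit". Section 7.2.2 places Visit 2 at 7 to 14 days after Screening and lists AE recording both before and after the first injection. A footnote to Table 2 sets an outer limit: "In principle, subjects are injected within 50 days after informed consent".

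**The concern.** A treatment-emergent table should contain what began, or got worse, once treatment started. A definition keyed to the date of recording can err in both directions. It can leave out a pre-injection AE that deteriorates after the injection. It can also take in an event that began before injection but was reported late.

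The omission matters more. Worsening after an intra-articular injection is a possible treatment effect and may differ between arms. If it does, the uncounted worsenings come mainly from the arm with more of them, and the table understates the difference. The count would also depend on whether a site edits the existing record or opens a new one.

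The second question is where history ends and AEs begin. Two sections say consent and one says screening. When Screening is spread over a washout, these are different dates.

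**Working it through.** The plan gives no figure on this point, so the check applies the written rules to each kind of event.

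| Event | Literal 13.4.4 | Onset-or-worsening rule |
|---|---|---|
| A. Begins after injection | Treatment-emergent | Treatment-emergent |
| B. Present when screened (history), worsens after injection | Treatment-emergent: 12.5.1.1 makes the worsening an AE, and it is recorded after injection | Treatment-emergent |
| C. Begins after Screening, recorded at the start of Visit 2, does not worsen | Not treatment-emergent | Not treatment-emergent |
| D. As C, but worsens after injection; site edits the existing record | **Not treatment-emergent** | Treatment-emergent |
| E. As D, but site opens a new record | Treatment-emergent | Treatment-emergent |
| F. Begins before injection, first recorded at Visit 3, does not worsen | **Treatment-emergent** | Not treatment-emergent |

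The two rules disagree in D and F. D and E are the same clinical event, separated only by data entry. The instruction in 12.5.4.1 to record each event separately does not say whether a worsening is a new event. Section 6.3 does not help: it names a treatment-emergent AE and a considerable worsening of an AE as alternatives, so worsening is not plainly part of the term.

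**Length of the exposed period** (consent to first injection). Inputs: Screening to Visit 2 is 7 to 14 days (7.2.2); drug washouts are 7 or 28 days (6.2, criteria 9 and 10). The sums assume that washout starts on the day of consent and that the 7 to 14 days run from the return visit.

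- No washout: 7 to 14 days.
- 7-day washout: 7 + 7 = 14 to 7 + 14 = 21 days.
- 28-day washout: 28 + 7 = 35 to 28 + 14 = 42 days.

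All lie within the 50 days in Table 2.

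**Weight of one subject.** With 40 subjects per arm (13.1), 1/40 = 2.5 percentage points of that arm's incidence. For the overall incidence this holds if the subject has no other treatment-emergent AE; for a preferred-term row, if there is no other record of that term.

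**History versus AE.** Take an event that starts during an in-study washout and persists at the return visit. Under 12.5.4.1 it is an AE, because consent has been signed. Under 11.6.1 it is not history, because it was absent at consent. Under 12.5.1.1 it is history if the subject counts as screened on the return visit, and an AE if on the first day. Section 7.2.1 does not say on which of those days baseline signs and symptoms are taken.

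**The case against.** The best defence is that the word for recording in 13.4.4 is loose wording for occurrence. Onset dates are collected (12.5.4.1, 12.5.4.3.1), and 13.4.4 itself classifies events by time of occurrence. On that reading row F disappears, and F also needs a report missed at the start of Visit 2. Row D remains, because onset alone does not capture worsening.

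Several other points also stand. Conditions present at screening are covered by the worsening clause. All recorded AEs are listed. Untoward changes in the target knee are reportable as AEs at any visit (12.1), and target knee examinations are summarised by arm. Randomization balances on site, so differing site habits alone should not create a difference between arms. None of this puts row D into the by-arm incidence table: a listing is not a comparison, and 12.1 does not say that a worsening needs its own record. Section 13.3 leaves some detail to a statistical analysis plan, but the text at hand contains no onset-based rule.

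A reader might infer three stronger things that the documents do not support:

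- *Harms of drug withdrawal vanish from AE reporting.* Recording starts at consent, history is fixed at consent in 11.6.1, AEs are recorded at Screening (7.2.1), and Table 3 foresees AEs that begin in the screening phase. One undated word in 12.5.1.1 points the other way. That is a conflict, not a rule that discards these events.
- *A knee-pain flare during washout that worsens after injection is certain to be missed.* If the flare is history, its worsening is an AE recorded after injection and is counted. It is missed only if the flare was already an AE and the site opens no new record.
- *Table 3 contradicts 13.4.4 in row F.* Causality and treatment emergence are separate questions, and an event can be treatment-emergent and not related.

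**Conclusion.** The point holds for a limited class of events. As written, 13.4.4 omits from the by-arm summary an AE first recorded before the first injection that worsens afterwards, unless the site happens to enter a new record. It also admits late-recorded events with earlier onset. This concerns the first-listed safety measure, and the text at hand does not close the gap.

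The size is modest and cannot be turned into a count. The documents give no rate of pre-injection AEs or of their worsening, and any assumed rate would be a guess. What can be said is that every subject is exposed for at least 7 days, and that one reclassified subject can move an arm's incidence by 2.5 points under the conditions shown.

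The conflict over the cut-off between history and AE is a lesser matter. Events arising in washout precede randomization, so how they are labelled does not bias the comparison of arms, and those that are recorded still appear in the listing. The conclusion rests on reading 13.4.4 literally.

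**What to change.** Three changes of wording:

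1. In 13.4.4, define a treatment-emergent AE as one with onset, or worsening in severity, at or after the start of the first injection. Naming the first injection also settles the singular.
2. In 12.5.1.1, extend the worsening clause to any AE that began before the first injection, and state that the worsening is entered as a new AE record with its own onset date and severity.
3. In 12.5.1.1, replace screening with informed consent as the boundary between history and AE, to match 11.6.1 and 12.5.4.1.

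Onset date and severity are already collected, so no new type of data, visit or procedure is needed. The cost is one extra AE entry per worsening, a line in the eCRF completion guidance, and slightly changed treatment-emergent counts: up where worsening is now counted, down where late-recorded earlier events are removed.
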